5.1.7 Supportive care guidelines and concomitant medications

Participants must be instructed not to take any additional medications, including over-the-counter products, during the trial without prior consultation with the investigator. All medications taken within 30 days of screening should be recorded. If concomitant therapy must be added or changed, including over-the-counter medications or alternative therapies, the reason and name of the drug/therapy should be recorded.

MEMORIAL SLOAN-KETTERING CANCER CENTER IRB PROTOCOL

IRB#: 14-177 A(5)

In general, the use of any concomitant medications/therapies deemed necessary for the care of the participant are allowed, including drugs given prophylactically (e.g. antiemetics) with the following exceptions:

- Strong CYP3A inhibitors and CYP3A inducers are prohibited. Moderate CYP3A inhibitor and inducers may be used with caution. In vitro studies suggest that buparlisib is a sensitive CYP3A4 substrate. Co-administration of buparlisib with strong and moderate CYP3A4 inhibitors is predicted to increase the systemic exposure to buparlisib; likewise CYP3A4 inducers can be expected to decrease systemic exposure to buparlisib, possibly resulting in sub-therapeutic drug levels. Please refer to Appendix 1 for a list of prohibited drugs. Please note that this list may not be comprehensive.
- CYP3A and CYP2C substrates are discouraged but may be used with caution and monitoring. Particularly, caution is advised when buparlisib is co-administered with drugs that are sensitive substrate or have a narrow therapeutic index. Participants receiving such medications must be monitored for potentiation of toxicity due to any individual concomitant medications, and may require dose titration or reduction of the drug substrate. Please refer to Appendix 2 for a list of drugs. Please note that this list may not be comprehensive.
- QT interval prolonging medications known to induce Torsades de Pointes or to promote QT prolongation are prohibited (see Appendix 3). If a participant, after initiating study drug, requires the concomitant use of a drug known to prolong the QT interval, then investigators, at their discretion, may co-administer such medications with appropriate monitoring. The Primary Investigator should be consulted as soon as possible
- Concomitant use of QT prolonging medications that have a conditional or possible risk to induce Torsades de Pointes is allowed with caution and monitoring (see Appendix 4)

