10.0 EVALUATION DURING TREATMENT/INTERVENTION

10.1 General Requirements

Table 6 describes the required procedures. All procedures may increase in frequency if clinically indicated or oriented following a toxicity/adverse event.

A complete history, vital signs (including blood pressure, pulse, respiratory rate, temperature, weight and height), physical and neurological examination (to include documentation of the patients Karnofsky performance status (Appendix 6) and NANO score as well as a serum pregnancy test for women of childbearing potential will be performed on day 1 (+/- 4 days) of each cycle.

Neuro-imaging (including contrast-enhanced MRI/CT brain and total spine) and/or CSF collection (for patients with CSF disease; through Ommaya or spinal tap; including cytology) will need to be performed on all patients on day 1 cycle 3, and each additional odd numbered cycle (+/- 4 days). Imaging will include only the side of active disease (MRI brain for patients with brain disease; MRI total spine for patients with intraspinal disease; MRI brain and total spine for patients with brain and spine disease as well as leptomeningeal disease) or sides suggested by new neurologic symptoms and signs. All MRI imaging will included MR perfusion . If MRI spectroscopy is additionally performed, we will collect the additional data.

CBC with differential, platelets, sodium, potassium, calcium, AST, ALT, alkaline phosphatase, total bilirubin, fasting plasma glucose, creatinine, will need to be performed at day 1 and day 15 of each cycle and at the end of the treatment (+/- 4 days).

Amylase and lipase need to be assessed at the end of the treatment (+/- 4 days).

Chest X-ray and 12-lead ECG need to be done every other cycle starting at day 1 of cycle 3 (+/- 4 days)

Participants need to complete the PHQ-9 and GAD7 self rating mood scale (see Appendix 6).at day 1 and day 15 of cycle 1 and 2. On each consecutive cycle only on day 1 and at the

**MEMORIAL SLOAN-KETTERING CANCER CENTER
IRB PROTOCOL**

IRB#: 14-177 A(5)

end of treatment (+/- 4 days). Questionnaires can be performed over the phone on Cycle 2 Day 15 by research staff, if the participant is not able to physically attend to clinic.

Table 6: Required Activity Calendar

Tests and procedures	Screening	On trial						
		Prior to Registration	Cycle 1		Subsequent cycles		End of treatment	30-day post drug
			Day 1	Day 15	Day 1	Day 15		
Informed consent	X							
Inclusion/exclusion criteria	X							

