11.9 Concomitant medications

In general, the use of any concomitant medication/therapies deemed necessary for the care of the patient is permitted (see Section Permitted concomitant therapy), except as specifically prohibited (see Section Prohibited concomitant therapy).

All medications (excluding study treatment and prior antineoplastic treatments), procedures and significant non-drug therapies (including physical therapy and blood transfusions) administered within 28 days prior to the administration of buparlisib through 30 days after the last dose of buparlisib will be recorded in the Concomitant medications. Medications include not only physician prescribed medications, but also all over-the-counter medications, herbal medications (prohibited, see Section below) and food or vitamin supplements. The investigator should instruct the patient to notify the investigational site about any new medications she takes after the start of the study drug.

The patient must be told to notify the investigational site about any new medications he/she takes after the start of the study drug. All medications (other than study drug) and significant non-drug therapies (including physical therapy and blood transfusions) administered during the study must be listed on the Concomitant Medications Sheet.

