11.10.6 Drugs with a conditional or possible risk to induce Torsades de Pointes

If a patient, after enrollment in the study, requires the concomitant use of any QT prolonging medication with a possible or conditional risk for Torsades de Pointes included in Appendix 4, then investigators, at their discretion, may co-administer such medications. Patients receiving such medications must however be closely monitored.

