11.10.8.6 Drugs with a known risk for Torsades de Pointes

If a patient requires the concomitant use of any medication included in Appendix 3 entitled "List of Prohibited QT prolonging drugs" (i.e., drugs that are generally accepted by the Qtdrugs.org Advisory Board of the Arizona CERT to have a risk of causing Torsade de Pointes), study treatment must be delayed. Note that Appendix 3 lists drugs with a known risk for Torsades de Pointes (TdP) as well as sensitive CYP3A substrates (with narrow therapeutic index) with a possible or conditional risk for TdP. Study treatment administration must be interrupted as long as the patient requires therapy with the QT prolonging agent.

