Appendix 3: Prohibited QT prolonging drugs with risk of Torsades de Pointes

All QT-prolonging drugs listed are prohibited for all patients from screening through permanent discontinuation of study treatment.

List of prohibited QT prolonging drugs

Drug	QT risk(*)	Comment
Amiodarone	Known risk for TdP	Females>Males, TdP risk regarded as low
Arsenic trioxide	Known risk for TdP	
Astemizole	Known risk for TdP	No Longer available in U.S.
Bepidil	Known risk for TdP	Females>Males
Chloroquine	Known risk for TdP	
Chlorpromazine	Known risk for TdP	
Cisapride	Known risk for TdP	Restricted availability; Females>Males.
Disopyramide	Known risk for TdP	Females>Males
Dofetilide	Known risk for TdP	
Domperidone	Known risk for TdP	Not available in the U.S.
Droperidol	Known risk for TdP	
Halofantrine	Known risk for TdP	Females>Males
Haloperidol	Known risk for TdP	When given intravenously or at higher-than- recommended doses, risk of sudden death, QT prolongation and torsades increases.
Ibutilide	Known risk for TdP	Females>Males
Levomethadyl	Known risk for TdP	
Mesoridazine	Known risk for TdP	
Methadone	Known risk for TdP	Females>Males
Pentamidine	Known risk for TdP	Females>Males
Pimozide	Known risk for TdP	Females>Males
Probucof	Known risk for TdP	No longer available in U.S.
Procainamide	Known risk for TdP	
Quetiapine	Possible risk for TdP	Prohibited as this drug is a sensitive 3A4 substrate
Quinidine	Known risk for TdP	Females>Males
Sotalol	Known risk for TdP	Females>Males
Sparfloxacin	Known risk for TdP	
Tacrolimus	Possible risk for TdP	Prohibited as this drug is a sensitive 3A4 substrate with narrow TI
Terfenadine	Known risk for TdP	No longer available in U.S.
Thioridazine	Known risk for TdP	
Vardenafil	Possible risk for TdP	Prohibited as this drug is a sensitive 3A4 substrate
(*) Classification according to the Qtdrugs.org Advisory Board of the Arizona CERT Sensitive substrates: Drugs whose plasma AUC values have been shown to increase 5-fold or higher when co-administered with a potent inhibitor of the respective enzyme. Note: drugs with a known risk for TdP that are also strong inhibitors of CYP3A are not repeated here and only mentioned in Appendix 2. Please also refer to http://crediblemeds.org/ for a comprehensive list of agents that prolong the QT interval		

MEMORIAL SLOAN-KETTERING CANCER CENTER
IRB PROTOCOL

IRB#: 14-177 A(5)

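### Section 5.1.7 most naturally reads as letting investigators give an Appendix 3 QT drug without holding buparlisib, whereas Section 11.10.8.6 requires an interruption; the ambiguity is unresolved and safety-relevant

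*Combined protocol and SAP*

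**What the plan says.** Five places in the combined protocol and SAP bear on this.

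- **Section 5.1.7, QT bullet, first sentence:** "QT interval prolonging medications known to induce Torsades de Pointes or to promote QT prolongation are prohibited (see Appendix 3").
- **Section 5.1.7, same bullet, next sentence:** once study drug has started, if a participant requires "a drug known to prolong the QT interval, then investigators, at their discretion, may co-administer such medications with appropriate monitoring". The bullet ends by asking that the Primary Investigator be consulted promptly. The bullet directly below it separately allows the conditional-risk and possible-risk drugs of Appendix 4, with caution.
- **Section 11.10.8.6**, on any Appendix 3 drug that becomes necessary: "Study treatment administration must be interrupted as long as the patient requires therapy with the QT prolonging agent".
- **Section 11.10.6** gives investigators discretion over QT drugs "with a possible or conditional risk for Torsades de Pointes included in Appendix 4, then investigators, at their discretion, may co-administer such medications".
- **Appendix 3, header:** "All QT-prolonging drugs listed are prohibited for all patients from screening through permanent discontinuation of study treatment".

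Section 11.9 adds that concomitant therapy is generally permitted "except as specifically prohibited (see Section Prohibited concomitant therapy").

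**The concern.** Take a participant on buparlisib who comes to need methadone or haloperidol, both listed in Appendix 3. An investigator working from Section 5.1.7 could give the drug, monitor, consult and carry on with buparlisib. An investigator working from Section 11.10.8.6 must stop buparlisib. The protocol does not say which section governs.

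The hazard is Torsades de Pointes. Appendix 3 itself warns that for haloperidol, given intravenously or above recommended doses, "risk of sudden death, QT prolongation and torsades increases". The two readings would also lead to different dosing of similar patients in a trial of 21.

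**Working it through.** There is no figure to reproduce. The check is a comparison of texts, with two small pieces of arithmetic.

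**1. Which drugs does the permissive sentence in Section 5.1.7 cover?** It names no appendix, so its scope has to be inferred. Three features point to Appendix 3:
- It sits inside the bullet that prohibits Appendix 3 drugs and follows that prohibition directly.
- It repeats the prohibition's wording: the prohibition covers drugs known to promote QT prolongation, and the permission covers a drug known to prolong the QT interval.
- Appendix 4 drugs have their own bullet immediately below. If the sentence were about them, it would be in the wrong bullet and would largely duplicate the next one.

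One feature points to Appendix 4. Section 11.10.6 uses almost the same sentence and expressly limits it to Appendix 4 drugs.

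**2. What follows under each reading?** Counting entries, Appendix 3 has 29 drugs (26 rated known risk, 3 possible risk) and Appendix 4 has 51 (33 possible, 18 conditional). No drug is on both lists.
- If the sentence covers Appendix 3, all 29 may be given without a hold under 5.1.7, and all 29 require a hold under 11.10.8.6.
- If it covers only Appendix 4, none of the 29 is affected and there is no conflict.

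**3. Does another section settle it?** Sections 11.9 and 11.10.8.6 and the Appendix 3 header all favour the hold. None mentions 5.1.7 or says that it yields.

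**4. Do other safeguards stand in for the hold?**
- The entry exclusions in Section 6.2 act before treatment. The sentence in 5.1.7 applies after it has started.
- The monitoring required by 5.1.7 has no stated ECG timing. The first scheduled on-treatment ECG is at day 1 of cycle 3 (Section 10.1 and Table 6). With 28-day cycles that is 2 × 28 = 56 days after the first dose, give or take 4 days, and then every 56 days. Section 10.1 adds that "All procedures may increase in frequency if clinically indicated", which allows extra ECGs but does not require them.
- Table 11 (Section 11.2) stops buparlisib for QTcF above 500 ms or a change above 60 ms on at least two ECGs. That acts after prolongation is seen, while 11.10.8.6 acts before.
- The consultation in 5.1.7 is to happen promptly. It is not a condition of giving the drug.

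These reduce the risk. None tells the investigator to hold buparlisib when the QT drug is started.

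**The case against.** The best defence is that the sentence was never meant for Appendix 3 drugs. Its close match with Section 11.10.6 suggests text drafted for Appendix 4 that ended up in the wrong bullet. The rest of the protocol points one way, and because 5.1.7 only permits, an investigator who holds buparlisib complies with every section. All of that stands. It is why the point is an ambiguity, and it also shows which rule the protocol intends. It does not remove the problem, because an investigator who relies on 5.1.7 has a natural reading that leads to the less safe action.

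A reader might try to close the question with the appendix ratings: no Appendix 4 drug is rated known risk, so a drug known to prolong QT cannot be an Appendix 4 drug. The documents do not support this. Those ratings grade the risk of Torsades, not of QT prolongation, and every drug in Appendix 4 is listed there as QT-prolonging. For the same reason, the number of known-risk Appendix 3 drugs still available in the U.S. would not measure exposure.

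**Conclusion.** The point holds as an unresolved, safety-relevant ambiguity. Read in its place, Section 5.1.7 permits co-administration of an Appendix 3 drug without holding buparlisib, against Section 11.10.8.6 and the Appendix 3 ban. This rests on inference from placement and wording, since the sentence names no appendix.

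A reader might go further and infer that the protocol authorises Appendix 3 drugs alongside buparlisib. The text does not support that: Section 11.10.6 offers a plausible alternative scope, and three other places favour the hold.

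The scope is all 29 Appendix 3 drugs or none, depending on the reading. The documents do not show how many of the 21 participants would need one, and the number may be zero. The sample size and the decision rule of at least 12 of 21 progression-free are unaffected. The wording should be corrected because it governs a safety action and the correction is cheap.

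**What to change.** In the Appendix 3 bullet of Section 5.1.7, replace the permissive sentence and the consultation sentence after it with:

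> If an Appendix 3 drug, or any other drug with a known risk of Torsades de Pointes (including those listed only as strong CYP3A inhibitors), becomes necessary after study drug has started, buparlisib must be interrupted for as long as that drug is required (Section 11.10.8.6). The Principal Investigator must be consulted as soon as possible for these drugs and for any QT-prolonging drug not listed in Appendix 3 or 4.

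The wider scope is needed because a note to Appendix 3 says it leaves out known-risk drugs that are strong CYP3A inhibitors, and sends the reader elsewhere for a full list. A replacement limited to listed drugs would remove the only on-treatment QT instruction and consultation step that 5.1.7 has for unlisted ones.

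Keep investigator discretion for Appendix 4 drugs, as in Section 11.10.6. Leave the Appendix 3 ban as it stands, adding at most a cross-reference to Section 11.10.8.6.

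The cost is possible extra dose interruptions. For Appendix 3 drugs, 11.10.8.6 already imposes them; for unlisted known-risk drugs they would be new. A hold of 28 days or more may lead to permanent discontinuation under Section 9.2. Section 9.1 lets the Principal Investigator make an exception for a patient who has benefited, but it is written for toxicity delays. Whether it covers a hold for a concomitant drug would need the Principal Investigator's decision.

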6.0 CRITERIA FOR SUBJECT ELIGIBILITY

The population consists of adult patients with relapsed or refractory primary central nervous system lymphoma (PCNSL) or secondary central nervous system lymphoma (SCNSL).

The investigator or designee must ensure that only patients who meet all of the following inclusion and none of the exclusion criteria are offered treatment in the study.

6.1 Subject Inclusion Criteria

Patients eligible for inclusion in this study have to meet all the following criteria:

- Participants must be able to understand and be willing to sign a written informed consent document.
- Subjects must be at least 18 years of age on the day of consenting to the study.
- Histologically documented PCNSL or SCNSL. Patients with SCNSL need to have cytology or tissue biopsy documenting lymphomatous involvement of the CNS
- Patients must have relapsed/refractory PCNSL or relapsed/refractory SCNSL
- All patients need to have received at least one prior CNS directed therapy. There is no restriction on the number of recurrences.
- Patients with parenchymal lesions must have unequivocal evidence of disease progression on imaging (MRI of the brain or head CT) 21 days prior to study registration. For patients with leptomeningeal disease only, CSF cytology must document lymphoma cells and/or imaging findings consistent with CSF disease 21 days prior to study registration.
- Participants must have a Karnofsky performance status (KPS) of ≥ 50 .
- Participants must have adequate bone marrow and organ function shown by:

MEMORIAL SLOAN-KETTERING CANCER CENTER IRB PROTOCOL

IRB#: 14-177 A(5)

- Absolute neutrophil count (ANC) $\geq 1.5 \times 10^9/L$
- Platelets $\geq 100 \times 10^9/L$ and no platelet transfusion within the past 14 days prior to study registration
- Hemoglobin (Hgb) ≥ 9 g/dL and no red blood cell (RBC) transfusion within the past 14 days prior to study registration
- International Normalized Ratio (INR) ≤ 1.5
- Alanine aminotransferase (ALT) and aspartate aminotransferase (AST) ≤ 1.5 times the ULN.
- Serum bilirubin \leq upper limit of normal; or total bilirubin $\leq 2.0 \times$ the ULN with direct bilirubin within the normal range in patients with well documented Gilbert Syndrome.
- Participants must be able to take oral medication.
- Patients must be able to tolerate MRI scans.
- Patients must be able to tolerate lumbar puncture and/or Ommaya taps.
- Participants must have recovered to grade 1 toxicity from prior therapy.
- Participants must be able to submit 20 unstained slides from the initial tissue diagnosis for confirmation of diagnosis and correlative studies
- Life expectancy of > 3 months (in the opinion of the investigator)

Note: Prior autologous stem cell transplant as well as radiation to the CNS is **NOT** an exclusion criterion. Prior allogenic stem cell transplant **IS** an exclusion criterion.

6.2 Subject Exclusion Criteria

Patients eligible for this study must not meet any of the following criteria:

- Patients with CNSL actively receiving treatment for extra-CNS disease are excluded. Patient should have complete resolution of their systemic disease not requiring additional systemic therapy (e.g. maintenance rituximab or decadron).
- The patient has received prior treatment with a PI3K inhibitor, AKT inhibitor, or mTOR inhibitor (e.g. rapamycin, MK2206, perifosine, etc.).
- Patient is concurrently using other approved or investigational antineoplastic agents
- Patient has received chemotherapy or targeted anticancer therapy, monoclonal antibodies ≤ 4 weeks or 5 half-lives, whichever is shorter, or 6 weeks for nitrosourea or mitomycin-C prior to starting the study drug, or the patient has not recovered side the side effects of such therapy
- Patient who has received wide field radiotherapy ≤ 4 weeks or limited field radiation for palliation ≤ 2 weeks prior to starting study drug or who have not recovered to grade 1 or better from related side effects of such therapy (except alopecia)
- Patient requires more than 8 mg of dexamethasone daily or the equivalent
- Patient is taking an enzyme inducing anti-epileptic drug (EIAED), including phenobarbital, phenytoin, fosphenytoin, primidone, carbamazepine, oxcarbazepine, eslicarbazepine, rufinamide, and felbamate. Participants must be off of any EIAED for a least two weeks prior to starting the study drug
- Patient is taking a drug known to be a strong inhibitor or inducers of the isoenzyme CYP3A. Participants must be off a strong CYP3A inhibitors and inducers for at least two weeks prior to starting the study drug.
- Patient is taking a drug with known risk to promote QT prolongation and Torsade de Pointes
- Patient is currently using herbal preparations or medications. Participants should stop using herbal medications 7 days prior to the first dose of the study drug.

MEMORIAL SLOAN-KETTERING CANCER CENTER IRB PROTOCOL

IRB#: 14-177 A(5)

- Patient is using warfarin or any other Coumadin-derivative anticoagulant. Patients must be off Coumadin-derivative anticoagulants for at least seven days prior to starting the study drug. Low molecular weight heparin is allowed
- Patient has a history of allergic reactions to compounds of similar chemical or biological composition to buparlisib
- Patient has an uncontrolled intercurrent illness, including, but not limited to, ongoing or active infection, chronic liver disease, chronic renal disease, pancreatitis, chronic pulmonary disease, or psychiatric illness or social situations that would limit compliance with the study requirements
- Patient has acute viral hepatitis or a history of chronic or active HBV or HCV infection
- Patient has an active concurrent malignancy requiring active therapy.
- Patient is known to have human immunodeficiency virus (HIV) infection
- Patient has any severe psychiatric disease that would interfere with participation in the trial as determined by the study investigator
- Patient has \geq CTCAE grade 3 anxiety
- Patient has \geq CTCAE grade 2 diarrhea
- Patient has a score ≥ 12 on the PHQ-9 questionnaire
- Patient selects a response of “1, 2 or 3” to question number 9 on the PHQ-9-questionnaire regarding potential for suicidal thoughts or ideation (independent of the total score of the PHQ-9).
- Patient has a GAD-7 mood scale score ≥ 15 .
- Patient has a medically documented history of or active major depressive episode, bipolar disorder (I or II), obsessive-compulsive disorder, schizophrenia, a history of suicidal attempt or ideation, or homicidal ideation (e.g. risk of doing harm to self or others).
- Patient has active cardiac disease or cardiac dysfunction including any of the following:
 - Left ventricular ejection fraction (LVEF) $\geq 50\%$ as determined by Multiple Gated Acquisition (MUGA) scan or echocardiogram (ECHO)
 - QTc >480 msec on screening ECG (using the QTcF formula)
 - Angina pectoris that requires the use of anti-anginal medications
 - Ventricular arrhythmias except for benign premature ventricular contractions
 - Supraventricular and nodal arrhythmias requiring a pacemaker or not controlled with medication
 - Conduction abnormality requiring a pacemaker
 - Valvular disease with documented compromise in cardiac function
 - Symptomatic pericarditis
 - Myocardial infarction within the last 6 months, documented by persistent elevated cardiac enzymes or persistent regional wall motion abnormalities on assessment of left ventricular ejection fraction function
 - History of documented congestive heart failure (New York Heart Association functional classification III-IV)
 - Documented cardiomyopathy
 - Congenital long QT syndrome
- Patient is currently receiving treatment with QT prolonging medication known to have a risk to induce Torsades de Pointes, and the treatment cannot be discontinued or switched to a different medication prior to starting study drug.
- Patient has impaired gastrointestinal function or gastrointestinal disease affecting absorption of buparlisib (e.g. ulcerative diseases, uncontrolled nausea, vomiting, diarrhea, malabsorption syndrome, or extensive small bowel resection).

MEMORIAL SLOAN-KETTERING CANCER CENTER IRB PROTOCOL

IRB#: 14-177 A(5)

- Patient has poorly controlled diabetes mellitus with a glycosylated hemoglobin >8% or poorly controlled steroid-induced diabetes mellitus with a glycosylated hemoglobin of >8%.
- Patient underwent major systemic surgery \leq 2 weeks prior to starting the trial treatment or who has not recovered from the side effects of such surgery.
- Women who are pregnant or nursing (lactating), where pregnancy is defined as a state of a female after conception until the termination of gestation, confirmed by a positive serum hCG laboratory test of > 5 mIU/mL.
- Patients who have received allogenic stem cell transplants.

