	
 ● instruct patient to follow dietary guidelines according to local and/or institutional standards for management of diabetes mellitus (such as those provided by the American Diabetes Association) during the study ● consider use of oral anti-hyperglycemic therapy such as metformin ● check FPG at least weekly for 8 weeks, then continue checking at least every 2 weeks if clinically indicated 
For non-fasting plasma glucose >500 mg/dL (> 27.8 mmol/L) accompanied by signs/symptoms of hyperglycemia (for example, mental status changes, excessive thirst, polyuria), or presence of blood or urine ketones, discontinue buparlisib and following guidance for management of Grade 4 fasting plasma glucose (FPG).

CARDIAC	
Cardiac - Left Ventricular systolic dysfunction	
Asymptomatic, resting ejection fraction 40-50%; or 10-20% drop from baseline	Maintain dose level, and continue buparlisib with caution Repeat LVEF within 4 weeks or as clinically appropriate
Symptomatic, responsive to intervention, ejection fraction 20-39% or > 20% drop from baseline	
 ● Omit buparlisib until resolved* (as defined below), then ↓ 1 dose level ● LVEF measurement to be repeated, if not resolved* within 21 days, permanently discontinue patient from buparlisib treatment
Refractory or poorly controlled, ejection fraction < 20%	● Permanently discontinue patient from buparlisib
*the event is considered resolved when the patient is asymptomatic, has a resting ejection fraction ≥ 40% and ≤20% decrease from baseline.	
Cardiac – QTc prolongation	
QTcF > 500 ms (≥ Grade 3) or > 60 ms change from baseline on at least two separate ECGs	
First Occurrence:
 
 ● omit buparlisib ● Perform an analysis of serum potassium and magnesium, and if below lower limit of normal, correct with supplements to within normal limits. Concomitant medication usage must be reviewed. ● Perform a repeat ECG within one hour of the first QTcF of > 500 ms or >60ms from baseline ● If QTcF remains > 500 ms or >60ms from baseline, repeat ECG as clinically indicated, but at least once a day until the QTcF returns to < 480 ms. Seek cardiologist input. ● Once QTcF prolongation has resolved, buparlisib may be restarted at a one lower dose level 
Second Occurrence:
 
 ● Permanently discontinue patient from buparlisib
Other Cardiac Events	
Grade 1 or 2	Maintain dose level

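### The LVEF exclusion in section 6.2 runs the wrong way: it bars LVEF of 50% or more and sets no lower limit for an asymptomatic patient

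*Combined protocol and SAP*

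**What the plan says.** Section 6.0 makes every exclusion binding: "only patients who meet all of the following inclusion and none of the exclusion criteria are offered treatment in the study". Section 6.2 repeats the rule at the head of its list: "Patients eligible for this study must not meet any of the following criteria".

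One entry in that list opens with "Patient has active cardiac disease or cardiac dysfunction including any of the following". The first item beneath it is "Left ventricular ejection fraction (LVEF) $\geq 50\%$ as determined by Multiple Gated Acquisition (MUGA) scan or echocardiogram (ECHO".

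The only other numerical statements about ejection fraction are in the left ventricular systolic dysfunction rows of Table 11 (section 11.2). The mildest row is "Asymptomatic, resting ejection fraction 40-50%; or 10-20% drop from baseline", for which dosing continues with caution. The next row covers 20-39% and calls for the drug to be withheld. The last covers values below 20% and calls for permanent discontinuation. A footnote sets the condition for recovery: "the event is considered resolved when the patient is asymptomatic, has a resting ejection fraction ≥ 40% and ≤20% decrease from baseline".

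**The concern.** An exclusion list names the conditions that keep a patient out. Under a heading about cardiac dysfunction, a reader expects LVEF below a threshold. The item gives LVEF at or above it, which reads like an inclusion requirement placed in the wrong list. That origin is an inference; the protocol does not state it.

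This is an eligibility and safety matter, not an analysis matter. Two things are at stake:

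- **Safety screening.** The protocol measures LVEF in everyone before treatment but gives no usable limit for judging the result. A patient with a substantially reduced LVEF and no symptoms or documented diagnosis could be registered without meeting any explicit LVEF exclusion.
- **Compliance.** Any enrolled patient with normal LVEF is, on paper, an eligibility violation. Section 15.1 requires a protocol-specific Eligibility Checklist, and section 16.1 provides for compliance audits at least twice a year, so the reversed item could be copied into the checklist or recorded as a violation.

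**Working it through.** No plan figure needs reproducing and no arithmetic applies. The check sets the relevant provisions side by side.

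**1. Is there another LVEF limit at entry?** The organ-function list in section 6.1 covers ANC, platelets, haemoglobin, INR, ALT/AST and bilirubin, but not LVEF. Section 6.2 contains the one item in question. Sections 6.1 and 6.2 therefore hold one LVEF limit in total, stated as ≥50% in the exclusion list.

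**2. Apply the item to three example patients.** These LVEF values are chosen for illustration. Each patient is asymptomatic and has no documented cardiac diagnosis.

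| Baseline LVEF | LVEF item as written (≥50% excluded) | LVEF item corrected (<50% excluded) | Table 11 band by EF value |
|---|---|---|---|
| 60% | Excluded | Not excluded | None |
| 45% | Not excluded | Excluded | 40-50%: dosing continues with caution |
| 35% | Not excluded | Excluded | 20-39%: drug withheld (the row is worded for symptomatic patients) |

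As written, the item gives the opposite of what its heading calls for in all three cases. Corrected, it agrees with the heading and with the direction of Table 11.

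**3. Do neighbouring items supply the missing lower limit?** They do so only in part. Heart failure counts only as "History of documented congestive heart failure (New York Heart Association functional classification III-IV". Valve disease counts only as "Valvular disease with documented compromise in cardiac function". Cardiomyopathy must be documented. None names an asymptomatic patient with a low LVEF.

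**4. Would a later test catch such a patient?** Section 8.1 requires ECHO/MUGA within 21 days of registration, and Table 6 marks it in the screening column only, so there is one scheduled measurement. Section 10.1 schedules a 12-lead ECG every other cycle from cycle 3 but no repeat LVEF. Table 11 prompts a repeat only once an LV event has occurred, and section 10.1 otherwise leaves extra tests to clinical need.

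**5. Where is the gap widest?** Table 11 tolerates cautious dosing at 40-50%, so the more serious gap is below 40%. A patient there could start 100 mg daily with an LVEF lower than the level Table 11 requires before dosing resumes after an LV event.

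**6. Could the symbol be a text-extraction fault?** The other comparison signs in section 6.2 point the sensible way (PHQ-9 ≥12, GAD-7 ≥15, QTc >480 msec). Signs do vary elsewhere. The heading of section 11.11.1.2 uses ≥ where Table 11 and section 11.11.1.3 use > for the same liver thresholds. The Grade 4 glucose row of Table 11 pairs >500 mg/dL with ≥27.8 mmol/L. Both variations change strictness, not direction, so neither resembles a reversed sign. An extraction fault remains possible but is not the likelier explanation.

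**The case against.** The strongest reply has four parts.

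- **The finding rests on one symbol read from a PDF.** This is fair as far as it goes. The sign must be confirmed in the source before anything is changed.
- **The heading already covers low LVEF.** Its list is introduced as inclusive, and Table 11 itself calls reduced ejection fraction systolic dysfunction, so a low-LVEF patient can be read as barred by the heading alone. This stands as a partial safeguard. However, the heading gives no number and leaves the cut-off to each investigator. If the heading bars low LVEF while the item bars LVEF of 50% or more, almost nobody is eligible, which confirms that the item is wrong.
- **Table 11 governs dosing on treatment, not entry.** This is correct. Its 20-39% row is worded for symptomatic patients, and its 40% level defines recovery jointly with absence of symptoms and a limited fall from baseline. Using 40% as a reference point for entry is this review's inference. The direction of Table 11, with low values as the hazard, does not depend on that inference.
- **Clinicians would spot the slip.** Most probably would: the screening result is available before dosing, and section 7.0 says an investigator-physician sees every patient. That lowers the chance of harm. It does not make the written rule correct, and the checklist actually used at registration is not in the documents.

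None of these offers a reading under which the item is right as it stands.

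**Conclusion.** The item is wrong as written. The protocol's single LVEF entry limit points in the wrong direction and leaves no numerical floor for an asymptomatic patient. It should be corrected, although informed readers may already be working around it.

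The size can be stated only in terms of the rules: one entry limit, reversed; one scheduled LVEF measurement; no stated lower limit at entry, against ≥40% for recovery from an LV event. With no LVEF data in the documents, neither the number of low-LVEF patients who might be admitted nor the number of paper violations can be estimated. The planned 21 patients, the threshold of 12 progression-free patients, the Table 14 interval for 12 of 21 (34.02% to 78.18%) and the analysis denominators do not change.

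The conclusion assumes that the source document carries the same sign as the text reviewed. The safety argument further assumes that the general heading is not being applied in practice as a numerical LVEF limit.

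**What to change.** 1. Confirm the sign in the source protocol.
2. Change the section 6.2 item to exclude LVEF <50% by MUGA or ECHO. Alternatively, delete it there and add LVEF ≥50% to the organ-function list in section 6.1. The medical lead should confirm that 50% is the intended cut-off.
3. Check that the Eligibility Checklist matches the corrected rule.

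The cost is a correction to one comparison sign, or the move of one line, plus the checklist check. Sample size, decision rule and analysis need no change.
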